- The primary objective of this proposal is to generate new hypotheses and data for future studies by evaluating the effect of HIRREM as supplemental care for subjects with a number of neurological, cardiovascular, and psychophysiological diseases. The primary analytic outcome to determine the effect and feasibility of HIRREM is HRV as measured by standard outcomes collected using a BIOPAC device for continuous recording of heart rate and blood pressure. This also allows calculation of mean arterial pressure and baroreceptor sensitivity. We anticipate a decrease in sympathetic activity and an improvement in sympatho-vagal balance manifested as an increase in HRV parameters.
- Secondary objectives of this proposal include evaluation of the effects of HIRREM on:
 - Autonomic nervous system functions, as manifested by blood pressure and heart rate. Another expected result of a decrease in sympathetic activity and an improvement of sympatho-vagal balance may be a decrease in heart rate and blood pressure.
 - Psycho-physiological functional outcomes as measured using a standardized measure of health status the (EQ-5D), the Center for Epidemiologic Studies Depression Scale (CES-D), the GAD-7 measure of anxiety, the Insomnia Severity Index (ISI), and the PTSD Check List for civilians or military service members (PCL-C, or PCL-M, respectively). We expect to see an improvement in these measures following HIRREM.
 - Metrics for specific disorders will be measured according to relevant currently accepted assessment tools. Some of the conditions for which treatment is anticipated and the corresponding evaluation tools are in Appendix A. We expect to see improvement in these measures.

- Weight will be measured at the enrollment visit (V1), completion visit (V2) and follow-up visit (V3) to determine the potential impact of HIRREM on weight.
- Reaction time will be measured using the clinical reaction time enrollment visit (V1), completion visit (V2) and follow-up visit (V3).

Research Design and Methods:

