This protocol is an assessment of the functional and physiological effects of HIRREM on neurological, cardiovascular, and neurophysiological disorders. It will be a non-randomized, open label, and unblinded before-and-after trial. The intention of this protocol is to evaluate the effect of HIRREM on an objective, physiological common denominator (HRV), across a variety of relevant conditions, as well as changes in clinical symptoms scales, to generate hypotheses and pilot data for investigation in future proposals. HIRREM will be offered as deemed potentially advantageous by the investigator. Patients will be recruited to receive eight to twenty HIRREM sessions in addition to their usual care. HIRREM sessions will be completed over a one month period. Measurements for the primary and secondary outcomes will be obtained at the initial visit and after completion of HIRREM therapy. A follow-up visit (V3) will be performed four to eight weeks after the completion visit (V2). This will consist of several representative questionnaires and surveys and a repeat of recording of blood pressure and heart rate using the BIOPAC device.

1) Subjects Selection Criteria:

Male and Female adults and children over the age of 11 years with a clinical diagnosis consistent with the aims of this proposal, who also meet the inclusion criteria outlined below and are interested in receiving HIRREM, will be enrolled. Subjects will be recruited by physician referral, word of mouth, and through advertisement. Physicians who want to inform prospective subjects about the availability of the research will be provided with copies of the IRB approved consent form and IRB approved ad which they may give to prospective subjects. The physicians do not obtain subjects' consent for the research or act as representatives of the investigators. Physicians provide prospective subjects with information about contacting investigators for information or enrollment; and/or seek or obtain the prospective subjects' permission for investigators to contact them. The participant must be able to provide informed consent.

Inclusion Criteria:

- Male and female adults and children aged 11 years and older.
- Subjects who are over the age of 18 must be able to give informed consent. Children must be able to sign an assent form and have a signed parental permission form.

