3) Number of HIRREM Sessions and Length of Study:

All baseline measures will have been collected during the enrollment visit. The period of active HIRREM will begin with an initial assessment to map the patterns of frequencies and amplitudes in the brain. Participants will typically then receive eight to twenty HIRREM sessions over a one month period. Based on objective data regarding brain patterns, evidence of progress with balancing of frequencies and quieting of amplitudes, along with clinical progress, HIRREM may be extended beyond 20 sessions. Participants may be given a brief break of one to two weeks before returning for additional sessions. HIRREM sessions typically are 1.5 hours in length. Participants may receive two HIRREM sessions during a half day period, and thus will spend an average of five half days getting HIRREM during the month. There will then be a post-HIRREM data collection visit (V2) no longer than two weeks after completion of the HIRREM during which outcome measures will be repeated and a follow-up visit (V3) 4-8 weeks after (V2).

a. Enrollment Visit:

Informed consent obtained, brief medical history obtained (Appendix B), and collection of baseline measures. This will occur prior to the start of HIRREM and will require about 45-60 minutes of time. When possible the completed medical history form may be requested and received prior to the enrollment visit.

b. Initial Half Day Session:

On the first day of HIRREM, the participant will have an assessment (about 60 minutes) to determine the pattern of frequencies and amplitudes in his/her brain which may be followed by the first and possibly second HIRREM sessions.

c. Remaining HIRREM Sessions:

Participants may receive two HIRREM sessions in a half day period for an anticipated average total of 10 HIRREM sessions per participant, with five half days spent during the month of HIRREM. Participants may receive up to 20 HIRREM sessions over the course of ten visits. In the event this is deemed appropriate and necessary, and for the benefit of the subject, (see above) the number of HIRREM sessions may be extended.

d. Treatment Completion Visit:

Participants will return for a study completion visit no longer than two weeks following completion of the HIRREM sessions, when post-intervention measures will be obtained. This visit will take 45-60 minutes.

e. Follow-Up Visit:

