Heart rate is measured as beat-to-beat intervals (RRI) recorded by pulse-wave recording, and will be analyzed using custom software developed by Matlab. Data can be loaded and viewed, and a subset of the data can be selected to avoid artifacts during device placement or removal. Outlier identification is performed by determining all IBIs which demonstrate a 30% difference from the mean of the previous four samples. Such outliers are removed from the data set. HRV statistics that are generated include mean, variance, SDNN, RMSSD, pNN50, VLF, LF, HF, TP, LF/HF, sample asymmetry, sample entropy, and coherence. All of the algorithms for computation of these parameters are derived from information or source code from the Physionet archive (Goldberger). Data are saved to Excel spreadsheets for further statistical analysis by study team members.

b. Blood Pressure (BP)

Blood pressure (BP) measurements will be taken with a finger cuff on two fingers of the left hand while lying down on an examination table.

c. Neuropsychological and Psycho-Physiological Function:

- i. The Center for Epidemiologic Studies Depression Scale (CES-D) is a standard paper and pencil depression scale which will help to assess this co-morbidity.
- ii. The EQ-5D is a brief, standardized measure of health status developed by the EuroQol Group, and is a paper and pencil survey providing a single index value for health status.
- iii. The Generalized Anxiety Disorder-7 (GAD-7) is a seven item screening tool for anxiety that is widely used in primary care.
- iv. The Insomnia Severity Index (ISI) is a seven parameter measure of insomnia.
- v. Post Traumatic Stress Disorder (PTSD) (Civilian and Military) is a checklist to measure stress severity due to a traumatic experience
- vi. Nausea /Dizziness Severity Scale is a screening tool to measure symptoms related to stomach problems

d. Disorder Specific Metrics

- i. These may vary across subjects depending on the underlying condition. The table in Appendix A contains some of the conditions to be included and the corresponding assessment tools to measure the effects of HIRREM. This list is not exhaustive and other conditions may be added at the discretion of the investigator. In the event a patient with an unlisted condition is enrolled a currently accepted assessment technique will be employed to collect both initial and final data.

e. Weight

- i. This will be measured using a standard scale.

f. Reaction Time

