Data will be analyzed using the most recent versions of SAS (SAS Institute, Inc., Cary, NC). Prior to performing analyses related to the hypotheses, histograms and descriptive statistics will be computed to examine the characteristics and distributions of the data. As detailed below, analytical methods will be conducted through generalized linear models that allow specification of appropriate distribution as well as various covariance types to ensure that inference tests can be interpreted conventionally. If required, nonparametric equivalents to the proposed methods will be used to analyze variables not well characterized by standard distributions. Unless otherwise stated, all relevant analyses will be two-tailed and $p < 0.05$ will be used to determine statistical significance. Because this proposal is designed to estimate effect sizes for future pilot and definitive trials, care will be taken to provide point estimates of effect size for each outcome along with corresponding 95% CI.

This primary objective of this protocol is to evaluate the effect of HIRREM in neurological, cardiovascular, and psychophysiological disorders as measured by standard HRV parameters. Also, a variety of secondary outcomes will assess the impact on functional and physiological measures (BP and HR), a number of standard disorder specific clinical measures, and subjective psychophysiological outcomes. The primary analysis will be examining group differences on the post-HIRREM measure while controlling for baseline levels (i.e., group treated as a fixed effect, with baseline scores entered as a covariate in a generalized model assuming a normal distribution and identity link). Changes in all secondary measures will be indexed using the GLM using the repeated measurements within each individual. The groups will be comprised of a collection of individuals from within the study with a common clinical disorder, although exploratory analysis will also evaluate for common effects in consecutively enrolled subjects.

Human Subjects Protection:

1) Consent and Assent

Written informed consent, or assent and parental permission will be obtained by the research staff from each competent subject.

2) Confidentiality and Privacy

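### Weight change is read as a possible HIRREM effect with no control group and no allowance for growth, although children from age 11 are eligible

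*Combined protocol and SAP*

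**What the plan says.** Five parts of the protocol bear on this.

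- **Objectives and Hypotheses.** Weight is listed for V1, V2 and V3, "to determine the potential impact of HIRREM on weight". No direction of change is predicted.
- **Inclusion Criteria.** Eligible subjects are "Male and female adults and children aged 11 years and older". No limit is set on the number or share of minors.
- **Data Collection and Process, e. Weight.** The whole description is "This will be measured using a standard scale". Height, body mass index and age-standardised scores are not mentioned.
- **Research Design and Methods.** The study is a "non-randomized, open label, and unblinded before-and-after trial".
- **Statistical Analysis.** "Changes in all secondary measures will be indexed using the GLM using the repeated measurements within each individual". Groups are formed by clinical disorder, with a further exploratory look across consecutively enrolled subjects. No age or growth term is named. The section promises a point estimate and 95% CI for every outcome, with a two-sided 0.05 threshold.

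**The concern.** In a before-and-after comparison without controls, the reference value for no effect is zero change. For a growing child that value is wrong, because weight rises over the follow-up with no intervention at all. An unadjusted within-person estimate in minors is HIRREM effect plus growth, and the growth part has a known sign.

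The stake is the estimate itself. The study exists to supply effect sizes and pilot data for later proposals. A disorder group containing many minors could supply a weight signal that is only growth. In a mixed group, growth could partly mask a loss among the adults. The size of the distortion rises with the share of minors, which the plan leaves open.

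**Working it through.** The plan gives no power, SD or expected change for weight, so there is no figure of its own to reproduce.

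**Follow-up time, from the documents.** Treatment: "HIRREM sessions will be completed over a one month period", taken as 4 weeks. V2: "no longer than two weeks after completion of the HIRREM", so 0–2 weeks later. V3: 4–8 weeks after V2.

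- V1 to V2: 4 + 0 = 4 to 4 + 2 = 6 weeks; midpoint 5.
- V1 to V3: 4 + 0 + 4 = 8 to 4 + 2 + 8 = 14 weeks; midpoint 11.
- The permitted break of one to two weeks before extra sessions would lengthen both.

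**Assumptions, not in the documents.** Growth of 3–5 kg/year; SD of within-person weight change 1.5–3 kg; children making up 5%, 10% or 20% of a pooled cohort; no effect of HIRREM and no change in adults.

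**Expected gain per child** = rate × weeks / 52.

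- Week 5: 3 × 5/52 = 0.29 kg; 5 × 5/52 = 0.48 kg.
- Week 11: 3 × 11/52 = 0.63 kg; 5 × 11/52 = 1.06 kg.

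**Chance that growth alone gives p<0.05.** With mean change d, SE = SD/√n and k = d/SE, a two-sided normal test rejects with probability Φ(k − 1.96) + Φ(−k − 1.96).

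Example: 30 children, SD 1.5 kg, week 11. SE = 1.5/√30 = 0.274. At 3 kg/year, k = 0.635/0.274 = 2.32 and the probability is 0.64. At 5 kg/year, k = 1.058/0.274 = 3.86 and the probability is 0.97.

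| Group | Visit | SD 1.5 kg | SD 3 kg |
|---|---|---|---|
| 30 children | week 11 | 0.64–0.97 | 0.21–0.49 |
| 30 children | week 5 | 0.18–0.42 | 0.08–0.14 |
| 10 children | week 11 | 0.27–0.61 | 0.10–0.20 |
| 300 pooled, 20% children | week 11 | 0.31–0.69 | 0.11–0.23 |
| 300 pooled, 10% children | week 11 | 0.11–0.23 | 0.07–0.09 |
| 300 pooled, 5% children | week 11 | 0.07–0.09 | 0.05–0.06 |

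Each range runs from 3 to 5 kg/year; the nominal value is 0.05. For the pooled rows d is the share of children times the gain per child: at 10%, 0.1 × 0.63 = 0.06 kg to 0.1 × 1.06 = 0.11 kg.

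**Is weight taken at V3?** The objectives say so, and the description of the follow-up visit says that post-intervention measures are repeated. Research Design and Methods describes V3 as questionnaires plus the BIOPAC recording and omits weight. If weight stops at V2, the week-5 figures apply, a little under half of those at week 11.

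**The case against.** The case for leaving the plan alone has real substance.

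- **A reader might infer that growth will be reported as treatment-related weight gain, or that young disorder groups are bound to show a significant one.** The documents support neither. The objective speaks only of a potential impact and predicts no direction. Nothing says how a change would be interpreted, no ages are given by condition, and every probability above is below 1.
- **The governing analysis is partly inferred.** The Statistical Analysis section does not name weight when it lists the secondary outcomes, and no text fixes kilograms as the scale. This stands as a caution. Still, the sentence on secondary measures is the only analysis text that could cover weight, and the only measurement described is a scale reading.
- **Adult change is uncontrolled too.** Subjects are asked to abstain from alcohol during and for three weeks after treatment, and are encouraged to discuss participation with their healthcare provider afterwards because medication needs may change. This stands. It would be wrong to infer that restricting to adults yields an effect of HIRREM, so the fix must not say so.
- **The larger probabilities rest on a favourable setting.** This stands. The condition-specific case series reported from this project had 10 subjects each, and a wider SD or the V2 visit lowers the figures considerably.
- **The GLM could include age.** It names no such term, and a baseline-age covariate would not by itself correct the reference value within a group of children.
- **The study is exploratory and HRV is primary.** True, and it limits severity. But estimates are what this study is meant to produce, and the bias is present whatever the p-value.

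**Conclusion.** The point holds, as a minor one. As written, the plan offers no way to separate growth from a HIRREM effect on weight in minors, and the resulting bias is toward gain. Under 3–5 kg/year it is roughly 0.3–0.5 kg per child at V2 and 0.6–1.1 kg at V3, provided that weight is measured at V3.

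Whether this would be visible depends on quantities that the documents do not give: growth rate, SD, group size and the share of children. It could matter in a disorder group made up largely of minors. In the full cohort with 5–10% children the bias is only about 0.03–0.11 kg at week 11 and would seldom be noticed. The absence of controls is the wider cause; growth is the component whose direction is known and which can be handled with data already collected.

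**What to change.** Add to the weight objective and to the Statistical Analysis section:

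> Within-person weight change is estimated in subjects aged 18 and over. For subjects under 18, weight is converted to an age- and sex-standardised score at each visit and reported separately and descriptively, without pooling with adults. Neither is read as a causal effect of HIRREM, because there is no control group.

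Reconcile the weight objective, which includes V3, with the account of V3 in Research Design and Methods, which does not mention weight.

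The cost is a few sentences and a standard conversion; the reference used for it should be named. No new measurement is needed, since date of birth and gender are on the screening form. The downside is slightly fewer subjects in the adult weight estimate.

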There has also been analysis of several subsets of subjects from this ongoing research project. A case series of subjects with symptoms of Post-Traumatic Stress Disorder (PTSD) was presented as a poster at the annual meeting of the International Society for Traumatic Stress Studies, and a manuscript has been submitted for possible publication. This case series (n=10) showed significant improvements in the symptoms of PTSD (PCL-Civilian scale), sleep (ISI), and depression (CES-D). An abstract based on analysis of outcomes for another case series (n=10) of subjects with physical trauma/TBI was submitted

for possible presentation at the 2013 meeting of the American Academy of Neurology (AAN), showing significant improvements found in the ISI, CESD, and PCL-C scales.

We anticipate that there will be beneficial effects on balance in the autonomic nervous system associated with HIRREM, and thus, believe that heart rate variability (HRV), which reflects balance in the autonomic signal to the heart, is a good objective measure, and represents a relevant outcome for this study, irrespective of the clinical condition. To that end, an additional abstract was submitted for possible presentation at the 2013 AAN meeting. This case series of consecutive subjects enrolled in the project, for a variety of clinical complaints (n=23), showed significant correlation between the brain pattern pre-HIRREM (temporal asymmetry at T3/T4) and a HRV parameter (RMS-SD). This provides support for our understanding regarding lateralization of autonomic function in the HIRREM assessment of surface EEG data.

Evidence of benefit for HIRREM in other conditions, prospectively gathered in a carefully monitored clinical environment through this proposal, can serve as a foundation for the pursuit of future randomized controlled pilot studies, and eventually larger randomized controlled clinical trials. The ultimate goal of this line of study is the development of HIRREM as a noninvasive therapy for a variety of clinical conditions.

Objectives and Hypotheses:

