Baroreflex sensitivity (BRS) for control of HR, heart rate variability (HRV) and blood pressure variability (BPV): Continuous BP and HR are acquired from noninvasive finger arterial pressure measurements and ECG for a minimum of 8 minutes in subjects lying down quietly. SBP and RR intervals (RRI) files generated via the data acquisition system (BIOPAC acquisition system and software, Santa Barbara, CA) at 1000 Hz are analyzed using Nevrokard SA-BRS software (Nevrokard Kiauta, d.o.o., Izola, Slovenia) for measures of BRS, HRV and BPV as follows: Frequency Method. Power spectral densities of SBP and RRI oscillations are computed by 512 points Fast Fourier Transform (FFT) and integrated over specified frequency ranges (LF: 0.04-0.15 Hz; HF: 0.15-0.4 Hz). A Hanning window is applied and the their squared-coherence modulus is computed if coherence is >0.5 as reported (16). The square-root of the ratio of RRI's and SBP powers is computed to calculate LF, HF alpha indices, which reflect BRS (16). Power of RRI spectra in LF, HF range (LF_{RRI} and HF_{RRI}) are calculated in normalized units and the ratio of LF_{RRI}/HF_{RRI} is used as a measure of sympathovagal balance (17). Power of SBP spectra calculated as LF_{SAP} is used as a measure of BPV. Sequence Method. BRS calculated by this method is based on quantification of sequences of at least three beats (n) in which SBP consecutively increases (UP sequence) or decreases (DOWN sequence), which are accompanied by changes in the same direction of the RRI of subsequent beats (n+1). The software scans the RRI and SBP records, identifies sequences, and calculates linear correlation between RRI and SBP for each sequence. If the correlation coefficient exceeds a pre-set critical value (0.85), the regression coefficient (slope) is calculated and accepted. The mean of all individual regression coefficients (slopes), a measure of sequence BRS, is then calculated for Sequence UP, DOWN and TOTAL. Time-Domain Analysis. Three time-domain parameters are used for hemodynamic variability (18, 19). HRV is determined by computing the standard deviation of beat-to-beat interval (SDRR) and the root mean square of successive beat-to-beat differences in R-R interval duration (rMSSD). BPV is the standard deviation of the mean arterial pressure (SDMAP).

ii. HRV Data Processing and Interpretation

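### The Matlab HRV step allows part of a trace to be selected by eye, with no window rule and no visit masking described, which leaves the pre/post HRV effect sizes open to an avoidable bias

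*Combined protocol and SAP*

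**What the plan says.** Research Design and Methods describes the design: "It will be a non-randomized, open label, and unblinded before-and-after trial". Objectives and Hypotheses makes HRV primary ("The primary analytic outcome to determine the effect and feasibility of HIRREM is HRV as measured by standard outcomes") and states the direction expected: "We anticipate a decrease in sympathetic activity and an improvement in sympatho-vagal balance manifested as an increase in HRV parameters". The background says that HRV "is a good objective measure, and represents a relevant outcome for this study, irrespective of the clinical condition".

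Section 5) a. describes two processing routes.

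- **i. HRV Data Acquisition.** Signals are recorded "for a minimum of 8 minutes in subjects lying down quietly" and analysed in Nevrokard, which yields SDRR and rMSSD among other measures. No selection of part of the record is described.
- **ii. HRV Data Processing and Interpretation.** Custom Matlab software is used: "Data can be loaded and viewed, and a subset of the data can be selected to avoid artifacts during device placement or removal". Beats are then removed as outliers by a fixed 30% rule, and "Data are saved to Excel spreadsheets for further statistical analysis by study team members".

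The plan does not say which route supplies the primary HRV value, who selects the subset, or whether that person can see the visit. The study identifier under Confidentiality and Privacy protects identity; nothing there hides the visit.

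**The concern.** HRV is the outcome that the protocol treats as objective in a study where everyone knows that treatment was given. One processing step in the Matlab route nevertheless rests on judgement: someone looks at the trace and may decide where the analysed data begin and end. The recording has a minimum length but no fixed analysed length, and the expected direction is known in advance. If the cut points were chosen even slightly differently at the enrollment visit (V1) and the completion visit (V2), the difference would be added to the estimated change.

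What is at stake is the study's main product. Sections 2) Number of Subjects and 6) Statistical Analysis say that the data are meant to give effect-size estimates, with confidence intervals, for planning later trials. A biased pre/post HRV estimate would carry over into that planning.

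**Working it through.** The plan gives no power calculation, standard deviation or expected HRV change, so there is no figure to reproduce. The text can be checked for safeguards, and the possible size can be illustrated under assumptions.

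**1. Safeguards in the text.**

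| Element | Stated? |
|---|---|
| Purpose of the selection | Yes: artifact at device placement or removal |
| Beat-level outlier rule | Yes: 30% from the mean of the previous four samples |
| Analysed window length | No (recording minimum of 8 minutes only) |
| Start point or limit on trimming | No |
| Who selects | No |
| Masking of that person to visit | None described |
| Route giving the primary HRV value | No |

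The 30% rule acts on single beats. It does not fix the window.

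**2. How far window choice can move RMSSD.** Assumptions, none from the documents: a record of 520 beats (8 minutes at 65 per minute); variability that drifts slowly within the record, with a log-scale SD of 0.1 to 0.3; the most favourable window always kept after treatment and a fixed central window before it; no true effect. This is the worst case for each trimming allowance. The mean shift in ln RMSSD was simulated; the percentage rise is exp(shift) − 1.

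| Beats kept of 520 | Share trimmed | Shift in ln RMSSD | Apparent rise in RMSSD |
|---|---|---|---|
| 495 | 25/520 ≈ 5% | 0.004–0.008 | 0.4–0.8% |
| 450 | 70/520 ≈ 13% | 0.011–0.023 | 1.1–2.3% |
| 325 (5 of 8 min) | 195/520 = 37.5% | 0.036–0.081 | 3.7–8.4% |

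**3. Effect on a pooled pre/post test.** Assume an SD of 0.4 for the change in ln RMSSD. The standardised shift is b = shift / 0.4. The false-positive rate is that of a two-sided 5% paired t-test with noncentrality b√n, at the planned n = 300 (√300 = 17.32).

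| Share trimmed | b | b√300 | False-positive rate |
|---|---|---|---|
| about 5% | 0.010–0.020 | 0.17–0.35 | 5.3–6.4% |
| about 13% | 0.028–0.058 | 0.48–1.00 | 7.6–16.8% |
| 37.5% | 0.090–0.203 | 1.56–3.51 | 34–94% |

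If the SD of change were 0.6, the last row would be 18–65%; if 0.3, it would be 55% to nearly 100%. The first row stays between 5.2% and 7.5% across those SDs. If selection does not depend on visit, the expected shift is zero.

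**4. Effect on the planned primary model.** Section 6) compares disorder groups on the post-HIRREM value with baseline as covariate. This was simulated with two groups of 50 and a baseline–post correlation of 0.6 (both assumed), and a post-visit shift of 0.2 SD of the HRV measure.

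| Shift | Group test rejects | Pooled pre/post test rejects |
|---|---|---|
| None | 5.0% | 5.2% |
| Same in both groups | 4.6% | 60% |
| One group only | 23% | 19% |

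A common shift cancels in the group contrast and appears in the pre/post estimate. A shift in one group alone affects both.

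**The case against.** The strongest reply is that the selection is optional and has a stated, narrow purpose. Artifact from fitting and removing a device sits at the ends of a record, and trimming the ends moves RMSSD by less than 1% even in the worst case above. This stands, and it is why a large bias should not be presumed. It does not close the point, because nothing in the text holds trimming to the ends or to a small share of the record.

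Second, a reader might infer that the primary result itself is biased because there is no control arm. The documents do not support that. The primary model compares disorder groups, so a trimming habit common to all groups largely cancels, and nothing in the plan gives a reason to expect trimming to differ by disorder. The pooled analysis of consecutive subjects is labelled exploratory. What remains exposed is the pre/post effect and its effect-size estimate, which Section 6) promises for each outcome.

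Third, a reader might infer that unmasked staff hand-pick the data. The documents do not say so. They are silent on who selects and what that person sees, and the Nevrokard route describes no selection at all. Since the plan does not say which route gives the primary value, one cannot assert that it passes through the selection step, nor rule that out.

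Last, the study generates hypotheses. That lowers the consequence but does not remove it, because effect sizes for later trials are its declared output.

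**Conclusion.** The point holds as a gap in safeguards. The Matlab route allows a viewed subset to be analysed with no window rule and no visit masking described, so visit-dependent trimming could bias the pre/post HRV effect. Its size cannot be calculated from the documents. Under the assumptions above it is close to zero when only a small part of the ends is trimmed, and material only if much of the record may be chosen freely and the choice depends on visit. A shift common to all disorder groups leaves the primary group contrast nearly untouched; one that differs by group does not. Nothing in the documents shows that such bias has occurred. This is a low-cost improvement to make, not a flaw that invalidates the study.

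**What to change.** Amend Section 5) a. ii. as follows.

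- Before a recording is opened, replace its label with a random code that hides the visit, one code per recording.
- Analyse a window of the same fixed length at every visit, starting a set time after recording begins, and move it only for an artifact that is logged.
- Lock each HRV value before the visit key is merged. Values need not wait for the follow-up visit (V3).
- State whether Nevrokard or Matlab gives the primary HRV value.
- Report a sensitivity analysis on the untrimmed record after the 30% outlier rule. That record may still contain placement artifact, so it is a check on the effect of selection and not a better estimate.

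The cost is a renaming script, a paragraph of protocol text and a little extra file handling, with no added burden on participants. Some recordings will need a logged window shift or give a shorter record. Because the background describes the project as ongoing with subsets already analysed, earlier recordings should be reprocessed in the same way where the raw files exist, or flagged as processed differently. With visit hidden and the window fixed, the expected shift from segment choice is zero and the pre/post test returns to its nominal 5%. The sample size does not change.
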